## 8 PROTECTION OF HUMAN SUBJECTS

Prior to study initiation, appropriate approvals will be obtained from relevant authorities overseeing the study, e.g., Institutional Review Boards or Data Protection Agencies.

### 8.1 Informed Consent

Informed consent is not needed for this registry-based study, as there is no intervention or interaction with subjects, and subjects will not be identified.

## 9 MANAGEMENT AND REPORTING OF ADVERSE EVENTS/ADVERSE REACTIONS

### Adverse Event (AE) and Product Quality Complaint (PQC) Reporting Language for Non-Interventional Study Protocols

#### Adverse Event and Product Quality Complaint Reporting

This is a non-interventional database study based on secondary use of data collected for other purposes. No administration of any therapeutic or prophylactic agent is required in this protocol. No reporting of individual adverse events or product quality complaints to regulatory agencies is planned for this database study because there is no access to individual patient/subject records and it is not possible to assess the causality of individual cases. The investigator should refer to their institution's policy or local laws and regulations regarding reporting of any suspected adverse reactions and product quality complaints.

Any health outcomes (if collected per section 7.3.2), including any that qualify as adverse events, will be summarized as part of any interim analysis (including safety analysis, if required) and in the final study report, which will be provided to regulatory agencies by the Sponsor as required. Any relevant safety information will be summarized and the Sponsor will include in the appropriate Periodic Safety Update Report (PSUR)/Periodic Benefit Risk Evaluation Report (PBRER) and/or Development Safety Update Reports (DSUR) if required.

## 10 PLANS FOR DISSEMINATING AND COMMUNICATING STUDY RESULTS

The primary results of this research study will be externally disseminated in a manuscript submitted to a peer-reviewed, scientific journal, abstract/presentation at a scientific conference or symposium, or results posted on the HMA-EMA Catalogue of Real-World Data. Any publication related to the study will need to be reviewed/approved by the Sponsor prior to submitting results externally. Any publication resulting from this work will adhere to the procedures and pre-specified analysis plans within this protocol. Any publication related to the study will need to be reviewed/approved by the Sponsor prior to submitting results externally.

PRODUCT: V501/V503	PROTOCOL/AMENDMENT VERSION NO.: V503-095-00-v3
REVOPS ID NO: NIS102781	CORE DRC APPROVAL DATE: 18MAR2024
EPIDEMIOLOGY NO.(PE STUDIES ONLY): 08039.022	

## 12 ANNEXES

### Annex 1 OVERVIEW OF POTENTIAL CONFOUNDING IN ASSESSMENT OF HPV VACCINE EFFECTIVENESS AGAINST JUVENILE-ONSET RRP

#### **Definitions:**

[figure not shown]
Study exposure: Maternal HPV vaccination with GARDASIL or GARDASIL 9, below called HPV vaccination.

Study outcome: Juvenile-onset recurrent respiratory papillomatosis.

Primary objective: Estimate odds ratio (OR) of JoRRP (yes/no) given HPV vaccination in biologic mother (yes/no).

Power: The study has >80% power to detect an OR of 3.0 with a lower bound of the 95% confidence interval of >1.33, assuming at least 120 cases of JoRRP are observed.

Main association of interest:

The hypothesis is that maternal HPV vaccination is negatively associated with the odds (likelihood) of JoRRP. Factors that may act as confounders to this association are considered, below. That is, factors associated with both exposure and outcome in such a way that an observed association between the two is partially or completely confounded. Given that causal HPV infections in cases of JoRRP are acquired vertically (from mother-to-child during delivery), many of the same factors considered here as confounders in evaluating the association between HPV vaccination and JoRRP are the same as those considered in evaluating the association between HPV vaccination and AoRRP.

#### **Potential confounders or effect modifiers:**

Factors that may be **associated with exposure/HPV vaccination** in Nordic countries:

##### **1. Socioeconomic status**

In studies evaluating factors associated with uptake of HPV vaccination in the Nordic region, low education and low-income level of parent(s) were found to be associated with lower vaccine uptake [37] [38]. Statistically significant associations (95% CIs excluded null) were observed when focusing on girls in the free of charge school-based program (hazard ratio

PRODUCT: V501/V503	PROTOCOL/AMENDMENT VERSION NO.: V503-095-00-v3
REVOPS ID NO: NIS102781	CORE DRC APPROVAL DATE: 18MAR2024
EPIDEMIOLOGY NO.(PE STUDIES ONLY): 08039.022	

[HR] or odds ratio [OR] estimates ranging from: 0.75 to 0.92 for low education and from 0.67 to 0.87 for low income in Denmark and Sweden, respectively) and the subsidized program in Sweden (HR=0.53 for low income and HR=0.32 for low education). Additionally, in Denmark, investigators assessed association between vaccine uptake and country of birth and found that uptake was significantly lower if born outside of Denmark (OR=0.49, 95% CI=0.42-0.57) [37].

## 2. Sexual behavior

In a Swedish study examining acceptability of HPV vaccination in young adult women (up to age 30), investigators found that subjects with >1 sexual partner, a below median age of sexual debut, and defining themselves as bisexual were more willing to accept HPV vaccination than comparison groups. Effect sizes (ORs) were modest, ranging from 1.15 to 1.69, but statistically significant. Investigators also found that subjects who self-identified as being at high risk of a sexually transmitted infection (STI) were more willing to accept HPV vaccination (OR=2.0, 95% CI=1.56-2.17) [39].

In this context, it is important to note that a wide body of literature has addressed the possibility of riskier sexual behavior after HPV vaccination receipt. In this case, sexual habits could act as a mediator of the association between HPV vaccination and RRP and should *not* be adjusted for. However, no substantial evidence exists that suggests uptake of HPV vaccination leads to riskier sexual behavior, whereas on the contrary many studies have found no indications of change in behavior [40] [41] [42] [43] [44] [45] [46] [47] [48].

## 3. Pregnancy delivery method

There have been no studies showing an association between method of delivery (vaginal versus cesarean section) and willingness to vaccinate against HPV in Nordic region or elsewhere. An association between method of delivery and HPV vaccination can therefore be questioned.

## 4. Maternal history of external genital warts

It is difficult a priori to exclude that individuals with a previous history of STI may have an interest in vaccination against an STI. This case might be particularly existent for subjects with own history of external genital warts, where the subject may then obtain vaccination against HPV/EGW which also incidentally protects against RRP. Therefore, there may be a positive association with previous sexual activity/previous EGW and likelihood of exposure in this study. However, the strength of the association is expected to be small-moderate.

## 5. Maternal smoking history

There have been no comprehensive studies showing an association between smoking habits and willingness to vaccinate against HPV in Nordic countries or elsewhere. An association between smoking and HPV vaccination can therefore be questioned.

PRODUCT: V501/V503	PROTOCOL/AMENDMENT VERSION NO.: V503-095-00-v3
REVOPS ID NO: NIS102781	CORE DRC APPROVAL DATE: 18MAR2024
EPIDEMIOLOGY NO.(PE STUDIES ONLY): 08039.022	

## Factors that may be associated with outcome/JoRRP diagnosis in Nordic countries:

### 1. Socioeconomic status

Lower socioeconomic status (of parents) has been found to be associated with elevated risk of JoRRP in studies conducted outside of the Nordic region. For example, in a large database of publicly and privately insured patients in the United States, investigators reported that incidence was higher in publicly insured patients compared with those with private insurance (3.21 vs 1.98 per 100 000, respectively) [9]. Also, in a Canadian cross-sectional study of JoRRP patients from the Hospital for Sick Children in Toronto, investigators showed that approximately half of patients were below the poverty line [49]. Considering that HPV 6 and 11 infection is the cause of most RRP cases, a potential explanation for these findings is that parents' socioeconomic status is associated with risk of cervical HPV infection. In a large study combining data from five separate case-control studies conducted in Spain, Columbia, and Brazil (n=1,184 women), investigators assessed risk factors for cervical HPV infection and reported statistically significant lower risk among women with higher levels of education and family income in all countries [50]. To our knowledge, there have been no studies showing an association between mother's country of birth and child's risk of JoRRP in Nordic region or elsewhere.

### 2. Sexual behavior

Causal HPV 6 and 11 infections in JoRRP cases are acquired vertically (mother-to-child), thus maternal sexual behavior, HPV infection/AoRRP risk is expected to be associated with elevated risk of JoRRP in children, i.e., considered a relevant proxy. A recent international systematic review focused on RRP risk factors concluded that information is limited, but supported that sexual behavior is important for AoRRP risk, which is relevant for JoRRP given that causal infections are acquired from the mother [51]. The review concluded that "compared with disease-free controls, patients with RRP have a significantly higher median number of lifetime sexual partners" but also acknowledged that additional studies have mixed findings and conclusive evidence is lacking. A small study including 25 AoRRP patients [52], which is cited in the review by Welschmeyer and Berke, reported an OR of 2.11 (95% CI=1.02-4.39) for AoRRP development in patients with more than 25 lifetime sexual partners versus in those with 0-5.

### 3. Pregnancy delivery method

Evidence is inconsistent regarding whether birth by cesarean section is protective against JoRRP [4] [53] [54]. In a Danish retrospective cohort study focused on evaluation of maternal characteristics associated with JoRRP, investigators did not report a statistically significant lower risk associated with cesarean delivery (elective cesarean, RR=0.86, 95% CI=0.27-2.76; acute cesarean, RR=0.73, 95% CI=0.26-2.02) [4]. However, in a separate US study [53], investigators reported that out of 109 JoRRP cases, only a single case (<1%) was delivered by cesarean section, while the expected cesarean section rate was between 10% and 25%. Similarly, in a more recent US study, out of 208 JoRRP patients where delivery method

PRODUCT: V501/V503	PROTOCOL/AMENDMENT VERSION NO.: V503-095-00-v3
REVOPS ID NO: NIS102781	CORE DRC APPROVAL DATE: 18MAR2024
EPIDEMIOLOGY NO.(PE STUDIES ONLY): 08039.022	

was known, it was reported that >90% were delivered vaginally, which is much higher than the 2018 US national average of 68% [54]. An exploratory aim of the current study is to assess potential risk factors of JoRRP, including method of delivery.

#### 4. Maternal history of genital warts

The lead risk factor for JoRRP is a maternal history of genital warts. Most children who develop RRP are born to mothers with genital warts [55]. In the same Danish retrospective cohort study cited above, children born to mothers with history of genital warts were found to have ~230-fold increased risk of JoRRP compared to children born to mothers without history of genital warts (RR=231.4, 95% CI=135.3-395.9) [4]. Investigators also reported that longer delivery ( $\geq 10$  hours versus  $< 10$  hours) was associated with a two-fold greater risk of JoRRP (RR=2.0, 95% CI=1.1-3.5), which suggests vertical transmission of HPV infection during delivery [4].

#### 5. Maternal smoking history

In the Danish retrospective cohort study cited above that focused on evaluation of maternal characteristics associated with JoRRP, investigators did not observe any association between maternal smoking status at first prenatal visit and risk of JoRRP (RR=1.00, 95% CI=0.55-1.82).

#### Conclusions on potential confounders:

**Socioeconomic status** (income/education) appears to be moderately-strongly associated with exposure; however, there have been no studies conducted in the Nordic region assessing association with outcome of JoRRP. Studies conducted in other regions (Canada and the U.S.) support an association and it is likely that an association also exists in the Nordic region. Country of birth has been found to be strongly associated with HPV vaccine uptake in Denmark but an association with JoRRP has not been assessed. In the interest of obtaining the best evidence, this association and association between socioeconomic status and JoRRP should be evaluated formally. It is therefore planned to include these factors as potential confounders in the analysis.

Regarding **sexual behavior**, the association with HPV vaccine exposure appears to be weak, whereas that with AoRRP (proxy for JoRRP) is stronger. In Sweden, riskier sexual behavior was positively associated with willingness to be vaccinated, and therefore bias (due to this confounder) may be expected to be towards the null. Although number of sexual partners cannot explicitly be adjusted for in the proposed register-based study, the analysis will include adjustment for income, education and smoking as a proxy for sexual behavior. Additionally, analyses will be performed separately considering history of genital warts prior to vaccination. Stratified analyses will also be conducted by age at vaccination, as minimal bias due to sexual behavior would be expected among those vaccinated at younger ages.

PRODUCT: V501/V503	PROTOCOL/AMENDMENT VERSION NO.: V503-095-00-v3
REVOPS ID NO: NIS102781 EPIDEMIOLOGY NO.(PE STUDIES ONLY): 08039.022	CORE DRC APPROVAL DATE: 18MAR2024

While at least some association between **method of delivery** and JoRRP appears likely, it is unknown if any association exists with vaccine uptake. This variable will therefore be explored as a potential confounder in the analysis.

Considering that **maternal history of external genital warts** is so strongly associated with outcome of JoRRP and likely lies on the causal pathway (i.e., maternal acquisition of HPV types 6/11, progression to EGW, and transmission of causal HPV infection to child during delivery), it may not be appropriate to adjust for this variable in evaluation of vaccine effectiveness. Stratified analyses will be performed according to maternal history of EGW prior to delivery (yes/no).

Finally, while **maternal smoking** will be explored as a potential confounder in the analysis, prior studies do not suggest it is a risk factor for JoRRP or show an association with willingness to vaccinate against HPV. However, smoking may serve as a proxy for risky sexual behavior, along with income and education.

PRODUCT: V501/V503	PROTOCOL/AMENDMENT VERSION NO.: V503-095-00-v3
REVOPS ID NO: NIS102781 EPIDEMIOLOGY NO.(PE STUDIES ONLY): 08039.022	CORE DRC APPROVAL DATE: 18MAR2024

## Annex 2 TABLE AND FIGURE SHELLS FOR RRP STUDY (PRIMARY OBJECTIVE)

Table 2 Characteristics of Study Population, JoRRP Cases, and Control Subjects (prepared separately for each country)

	Study population, No. (%)	JoRRP cases, No. (%)	Controls, No. (%)
Age of child , years, mean (SD)			
Age of mother at delivery , years, mean (SD)			
Highest level of education achieved by mother*			
Low			
Medium			
High			
Missing			
Highest annual household family income level‡			
Low			
Medium			
High			
Missing			
Mother's country of birth			
Current country of residence			
Other country			
Missing			
Method of delivery			
Vaginal			
Cesarean			
Missing			
Maternal history of EGW			
Yes			
No			
Missing			
Maternal smoking status at first prenatal visit			
Yes			
No			
Missing			

EGW = external genital warts; JoRRP = juvenile-onset recurrent respiratory papillomatosis; SD = standard deviation

\*Education level of mother at index date.

‡Based on average level between 2006 (the start year of HPV vaccination) and the index date.

PRODUCT: V501/V503	PROTOCOL/AMENDMENT VERSION NO.: V503-095-00-v3
REVOPS ID NO: NIS102781	CORE DRC APPROVAL DATE: 18MAR2024
EPIDEMIOLOGY NO.(PE STUDIES ONLY): 08039.022	

Table 3 Number of Cases and Odds Ratio for Recurrent Respiratory Papillomatosis (RRP) by GARDASIL/GARDASIL 9 Vaccination Status, 2008-2020

GARDASIL/ GARDASIL 9 vaccination status	JoRRP (ICD-10 code: D14.1)			
	No. of cases 	No. of controls 	Crude OR (95% CI)	Adjusted OR  (95% CI)
Fully Vaccinated 			Ref.	Ref.
Unvaccinated				

*CI = confidence interval; HPV = human papillomavirus; ICD-10 = international classification of disease, 10th modification; JoRRP = juvenile-onset recurrent respiratory papillomatosis; OR = odds ratio; Ref. = reference.*

 All study participants who acquired a first diagnosis of D14.1 before age 10 years and appropriate topography/morphology code (if available from pathology/cancer registry).

 Up to 100 controls matched on age of mother, sex of subject, and region of diagnosis.

 Adjustment factors considered for inclusion include maternal education level, family income level, maternal smoking status, mother's country of birth, and method of delivery.

 A mother who received 3 doses (or 2 doses administered at 0 and 6-12 months if <15 years of age) of GARDASIL or GARDASIL 9 one year prior to delivery, without history of genital warts prior to vaccination, will be classified as exposed.

### Notes on Table 3:

1. In countries where topography/morphology codes cannot be obtained from pathology or cancer registry, separate tables will be prepared with outcome defined using: a) subcode D14.1.A, and b) code D14.1 and/or subcode D14.1A with at least one appropriate procedural code, i.e. DQB10 (Endoscopic extirpation), UDQ25 (Microlaryngoscopy with biopsy), and/or UDQ22 (Microlaryngoscopy).
2. Separate tables will be prepared: a) considering age at vaccination (<17 years vs. ≥17 years), b) considering time since vaccination of mother (≤10 years vs >10 years), c) considering maternal history of genital warts prior to delivery (yes/no), and d) irrespective of maternal history of genital warts prior to delivery/vaccination. In the event that there are <5 counts in an individual cell of any stratified table, it will not be possible to include exact counts due to strict data protection regulation in Europe.
3. Separate tables will be prepared with exposure defined as receiving at least one dose of GARDASIL/GARDASIL 9 vaccine.
4. Separate tables will be prepared focusing on GARDASIL use only as exposure.

PRODUCT: V501/V503	PROTOCOL/AMENDMENT VERSION NO.: V503-095-00-v3
REVOPS ID NO: NIS102781	CORE DRC APPROVAL DATE: 18MAR2024
EPIDEMIOLOGY NO.(PE STUDIES ONLY): 08039.022	

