### 3 AMENDMENTS AND UPDATES

Update no	Date	Section of Study Protocol	Amendment or Update	Reason	CORE DRC Approval Date	CORE DRC Version No
1	30Jun23	4	Updated data collection and final report timelines.	Revised milestones from PIs regarding data acquisition from respective registries.	27Jul23	2
		7.1	In Study Design Section of protocol, it was stated that “cases and controls will be matched as closely as possible on age of mother” without specifying age difference. The protocol has been updated to specify in this section that age difference will be +/- 1 year.	Additional information added on matching criteria (maternal age) of cases and controls.	27Jul23	2
		7.1	In Study Design Section of protocol, it was stated that “cases and controls will also be matched on calendar year of diagnosis and according to length of follow-up in the registries.” The protocol has been modified, removing mention of matching on “length of follow-up in the registries.”	Investigators will not explicitly match on number of years of follow-up.	27Jul23	2

PRODUCT: V501/V503	PROTOCOL/AMENDMENT VERSION NO.: V503-095-00-v3
REVOPS ID NO: NIS102781 EPIDEMIOLOGY NO.(PE STUDIES ONLY): 08039.022	CORE DRC APPROVAL DATE: 18MAR2024

Update no	Date	Section of Study Protocol	Amendment or Update	Reason	CORE DRC Approval Date	CORE DRC Version No
		7.2.2, 7.7.1	Exclusion criteria was added specifying that subjects/children whose mother received Cervarix (bivalent HPV vaccine) will be excluded from the study.	Cervarix does not target HPV types 6/11 and so not expected to prevent RRP.	27Jul23	2
		7.2.2	Added specific exclusion criteria that any child (case or control subject) who previously received any HPV vaccine will be excluded from analysis.	Focus of analysis is assessment of maternal vaccination in prevention of JoRRP.	27Jul23	2
		7.2.3, 7.3.1, 7.7.2	Inclusion of stratification according to time since vaccination of mother to $\leq 10$ years and $> 10$ years.	Attempt to explore durability of protection.	27Jul23	2
		9	Reference to Outcomes Section number was previously incorrect ("7.6.2" replaced with "7.3.2" in revised draft).	Correction of minor typographical error.	27Jul23	2
		6.2, 7.4, 7.7.3	Added exploratory objective to assess mother-child pairs, according to JoRRP and AoRRP history.	Explore concordant and discordant pairs according to RRP history	27Jul23	2

PRODUCT: V501/V503	PROTOCOL/AMENDMENT VERSION NO.: V503-095-00-v3

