## 7 RESEARCH METHODS

### 7.1 Study Design

#### Nested case-control study (primary objective)

**Setting:** Sweden, Norway, and Denmark.

In 2006, the U.S. Food and Drug Administration and European Medicines Agency approved the use of GARDASIL. National HPV vaccination programs in Scandinavian countries (Denmark, Norway, and Sweden) were instituted in subsequent years (~2008 or afterward) for young female adolescents, with catch-up vaccination programs for cohorts of older adolescents, teens, and/or young women in Denmark and Sweden. In Denmark, GARDASIL

PRODUCT: V501/V503	PROTOCOL/AMENDMENT VERSION NO.: V503-095-00-v3
REVOPS ID NO: NIS102781	CORE DRC APPROVAL DATE: 18MAR2024
EPIDEMIOLOGY NO.(PE STUDIES ONLY): 08039.022	

was used from October 2008 to February 2016, Cervarix (recombinant HPV bivalent [types 16 and 18] vaccine) from February 2016 to November 2017, and GARDASIL 9 since November 2017 (currently in use). The national HPV vaccination program targeting girls aged 12 years (primary cohort) was introduced in 2009, with fully subsidized catch-up vaccination for girls 13-15 years of age available since 2008, and girls/women up to 27 years of age since 2012. In Sweden, national HPV vaccination program using GARDASIL was introduced in 2010, with large-scale vaccination and high coverage achieved in 2012, with GARDASIL 9 being used since 2020. Fully subsidized catch-up vaccination for girls aged 13-17 years has been available in Sweden since 2012, and partially subsidized for the same age group since 2007. In Norway, the HPV vaccination program was initiated in 2009, in which girls approximately 12 years of age were offered GARDASIL in a three-dose schedule (until 2017). Catch-up vaccination was offered in Norway during the period 2016–2019 to women born between 1991 and 1996. Since 2017, Cervarix has been used in Norway. In 2015, a 2-dose schedule (with doses administered at 0 and 6 months) was recommended for females  $\leq 14$  years of age in Denmark and Sweden.

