In all Nordic countries, registries have been established to capture disease and vaccination history, as well as other demographic data. Importantly, all registry data can be linked by a unique PIN that is assigned to each resident at birth (or at the time of immigration) and does not change through the resident's lifetime. Therefore, existing infrastructure and registry systems are an excellent resource for monitoring the burden of HPV-related disease in the general population. The ability to link registry information for children and their mothers in Sweden, Norway, and Denmark enables assessment of vaccine effectiveness against JoRRP, i.e., maternal vaccination status prior to delivery can be compared between case and control subjects. Registries are accurate, complete, and have high population coverage, thereby minimizing some biases inherent in observational studies, such as selection of the study population, recall bias, and lack of access to complete medical records.

**Design:** Population based case-control study nested within a cohort of children born to mothers with opportunity to be vaccinated with GARDASIL/GARDASIL 9 at least one year prior to delivery. A nested case-control design allows the selection of controls from the same underlying population at risk as the cases, therefore reducing confounding and selection bias. This design is used for studies of rare diseases and is particularly advantageous for studies of biologic precursors of disease [28].

**Cohort:** GARDASIL was not available in eligible Nordic countries (Sweden, Norway, and Denmark) until late 2006, therefore we plan to capture the cohort of children (0-9 years) born to mothers' during the period 2008 to 2018 or later (birth cohorts 2008 to 2018+), i.e., JoRRP cases whose mother had opportunity to be vaccinated prior to becoming pregnant. The most recent registry data available from each country will be collected, e.g., 2018 or later. In the sections below, 2020 is listed as end date of follow-up period; however, the most recent data available in each country will be used.

**Cases:** Within the specified cohort, JoRRP cases (first diagnosis) will be identified from national registries using the ICD-10 code D14.1 (benign neoplasm of larynx). In countries

PRODUCT: V501/V503	PROTOCOL/AMENDMENT VERSION NO.: V503-095-00-v3
REVOPS ID NO: NIS102781	CORE DRC APPROVAL DATE: 18MAR2024
EPIDEMIOLOGY NO.(PE STUDIES ONLY): 08039.022	

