### 7.2.3 Stratification

Stratified analyses, statistical adjustment, and/or assessment of interaction will be performed for the primary objective according to the following factors:

- 1) Age at vaccination of mother (before 17 years of age vs 17 years or older)
- 2) Time since vaccination of mother ( $\leq 10$  years vs  $> 10$  years)
- 3) Maternal history of external genital warts prior to delivery (yes/no)

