Potential confounders such as mode of delivery, as well highest level of family income and education achieved by the mother (tentatively in tertiles relative to the general age-matched population in each of the respective countries) will be adjusted for when investigating the primary objective, through inclusion in the conditional logistic regression. Sensitivity analyses will be conducted in relation to the primary objective to assess the impact of: vaccine exposure definition (fully vaccinated versus  $\geq 1$  vaccine dose), age at vaccination ( $< 17$  years versus  $\geq 17$  years), outcome definition (ICD-10 code D14.1 versus cases [of D14.1] that have at least one associated treatment/procedural code and/or specified with subcode D14.1.A/“larynx papilloma”), time since vaccination ( $\leq 10$  years versus  $> 10$  years), and maternal history of EGW prior to delivery (yes versus no). To assess if older vaccinated women are a higher risk group, history of genital warts will also be presented separately among vaccinated women (i.e., history of genital warts prior to vaccination), stratified according to attained age at time of vaccination and compared with history of genital warts among unvaccinated women with same attained age. In the analysis, the group of women with history of genital warts prior to vaccination will be considered separately, if appropriate, i.e., assuming history of genital warts is not strongly associated with HPV vaccine uptake. If vaccination is found to be effective in preventing JoRRP among children whose mother had history of EGWs prior to delivery then it would suggest that vaccination not only prevents acquisition of infection in the mother but also prevents transfer of infection from infected mother to child, e.g., through maternal transfer of antibodies or other mechanism. OR estimates from the regression model will be inspected in terms of point estimates and precision, for comparison with results from the main analysis. Effect size (OR) estimates are expected to vary across most sensitivity analyses. For example, effectiveness may be higher among females that are fully vaccinated, vaccinated at younger age (prior to sexual debut), and without history of EGW.

There will be no adjustment for multiple comparisons in this study. Analyses have been pre-specified, discriminating between primary and sensitivity analyses, and all results will be reported.

PRODUCT: V501/V503	PROTOCOL/AMENDMENT VERSION NO.: V503-095-00-v3

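### The one-way durability table (time since vaccination ≤10 vs >10 years) is strongly confounded with age at vaccination and can hide or reverse waning

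*Protocol*

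**What the plan says.** Annex 2 fixes how Table 3 will be repeated. Note 2 asks for separate tables, one "considering age at vaccination (<17 years vs. ≥17 years" and another "considering time since vaccination of mother (≤10 years vs >10 years". Section 7.8.2 lists the same two splits as separate sensitivity analyses. Section 7.2.3 lists "Time since vaccination of mother" beside age at vaccination as a stratification factor. The amendment log gives the purpose of the time split: "Attempt to explore durability of protection". Nothing crosses the two factors, and footnote 3 of Table 3, which names the candidate adjustment variables, leaves out age at vaccination.

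Section 7.8.2 says that effectiveness may be higher in women "vaccinated at younger age (prior to sexual debut", and section 7.5 says the same of earlier Nordic results.

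On timing, section 7.1 states that "GARDASIL was not available in eligible Nordic countries (Sweden, Norway, and Denmark) until late 2006". It dates the extension of subsidised Danish vaccination to "girls/women up to 27 years of age since 2012", and adds: "Catch-up vaccination was offered in Norway during the period 2016–2019 to women born between 1991 and 1996".

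**The concern.** A table meant to show whether protection lasts should compare mothers who differ in time since vaccination and are otherwise alike. Here the programme calendar makes the two groups differ in age at vaccination as well, and the protocol itself expects age at vaccination to change effectiveness. The >10-year group is weighted towards women vaccinated as girls, while the ≤10-year group mixes girls with adults. The expected bias favours the >10-year group, so real waning can look like stable or even rising protection. The age-at-vaccination table has the mirror problem, because it carries a difference in time since vaccination. A different cut-point would not cure this. At stake is a conclusion about duration of protection, not the primary odds ratio.

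**Working it through.** **1. The plan's own figures.** Section 7.5 equates effectiveness of 38%-88% with odds ratios of 1.6-8.3 (unvaccinated against vaccinated). 1/(1 − 0.38) = 1.61 and 1/(1 − 0.88) = 8.33, so this reproduces. Section 5 says girls aged 10-13 in 2007 reach 23-26 in 2020. 10 + 13 = 23 and 13 + 13 = 26, so this reproduces too.

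**2. Who can exceed 10 years.** Maximum years since full vaccination = end of data − (programme start + 0.5), with 0.5 year for the 0-6 month schedule and the end of 2020 taken as 2020.99. Dates and ages are from section 7.1.

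| Group | Start | Maximum years at end of 2020 |
|---|---|---|
| Sweden 13-17, part-subsidised | 2007 | 13.5 |
| Denmark 13-15 | Oct 2008 | 11.7 |
| Denmark age 12 | 2009 | 11.5 |
| Norway about age 12 | 2009 | 11.5 |
| Sweden 13-17, fully subsidised | 2012 | 8.5 |
| Denmark up to 27 | 2012 | 8.5 |
| Norway catch-up, born 1991-1996 (age 20-28 in 2016-2019) | 2016 | 4.5 |
| Outside the programmes, any age | late 2006 | 13.6 |

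The programme groups that can pass 10 years were vaccinated at about 12-17. The two adult catch-up groups cannot pass it. With a 2020 end this holds whether time runs to delivery or to diagnosis, which the protocol does not state.

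**3. A link that does not depend on the calendar.** Measured to delivery, time since vaccination = mother's age at delivery − her age at vaccination. For a mother delivering at age a, more than 10 years means vaccinated before a − 10. At a ≤ 27, every >10-year mother was vaccinated before 17. At a ≥ 27, every ≤10-year mother was vaccinated at 17 or later. Controls are matched on maternal age within 1 year (section 7.1), so the tie operates inside each risk set.

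**4. Size, under assumed shares.** Let w and v be the shares vaccinated older in the ≤10-year and >10-year groups, with equal baseline risk.

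- With no waning and effectiveness of 88% (young) and 38% (older), the spurious gain with time is (w − v) × (88 − 38) points. For w = 0.5, v = 0 it is 25 points (63% against 88%). For w = 0.5, v = 0.2 it is 15 points (63% against 78%).
- With true waning in young-vaccinated mothers from 88% to 70%, w = 0.5 and v = 0, the ≤10-year table shows 0.5 × 88 + 0.5 × 38 = 63% and the >10-year table 70%, an apparent gain. Within mothers vaccinated <17 the same data show 88% and 70%.
- Break-even w (v = 0) for waning from 88% to 75%, 70% or 60%: 13/50 = 26%, 18/50 = 36%, 28/50 = 56%. Above these shares the fall is reversed.
- With milder odds ratios of 4.0 (young) and 1.6 (older), the ≤10-year value is 1/(w/1.6 + (1 − w)/4.0): 2.76, 2.29 and 1.82 for w = 0.3, 0.5 and 0.8. The >10-year table shows 4.0 without waning, or 2.0 if effectiveness fell from 75% to 50%.

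**5. Precision.** With 200 cases, an odds ratio of 3 and coverage c (section 7.5), the vaccinated share of cases is (c/3)/(1 − c + c/3). This is 1.7% at c = 5% and 3.6% at c = 10%, so 3.4 to 7.1 vaccinated cases in total.

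**The case against.** A reader might infer that the two factors are fully aliased and that only women vaccinated as girls can reach more than 10 years. The documents do not support that.

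- Section 7.4 takes out-of-programme doses from the Danish and Swedish prescription registries. Such women can be any age and, vaccinated from late 2006, can pass 10 years by 2020. Their number is not given, and they could be a material part of the >10-year group: a woman vaccinated at 18-19 in 2010 is 28-29 in 2020, close to the mean age at first birth of about 29 that the protocol cites.
- Swedish 17-year-olds fall in the ≥17 stratum.
- Mothers vaccinated <17 occur in both time groups, so the effects can be separated there.
- Section 7.1 uses the latest data available. Danish catch-up mothers could pass 10 years from about mid-2022 (2012 + 0.5 + 10). A child born then would be at most 2.5 years old at the end of 2024, early in the 2-4 year peak of onset, so the effect is limited if time runs to delivery.
- Norway has used Cervarix since 2017 and section 7.2.2 excludes mothers who received it, so part of the Norwegian catch-up may not enter. The Danish group carries more of the argument.

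All of this stands and rules out a claim of complete aliasing. None of it breaks the tie in step 3.

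It can also be said that section 7.2.3 permits stratification, adjustment and/or interaction, and that a SAP may settle which. That is fair, but section 7.2.3 does not commit to crossing the factors, while section 7.8.2 and Annex 2 do set one-way analyses. Ordinary adjustment is also awkward, since unvaccinated mothers have no age at vaccination.

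The strongest objection is precision. With 3-7 vaccinated cases, neither waning nor a false gain would be distinguishable, a full four-cell model is hardly estimable, and note 2 withholds exact counts below 5. This stands and limits both the harm and the remedy. Finally, among mothers vaccinated at 12-16, more than 10 years means delivery after about 22-26, so the stratified contrast still follows maternal age. Matching handles baseline risk in each odds ratio, but not a vaccine effect that itself varies with maternal age.

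**Conclusion.** The point holds as strong confounding, not aliasing. The planned one-way time table cannot be read as durability, because on the protocol's programme dates and its nominal 2020 end the >10-year group is weighted to vaccination at about 12-17 and the ≤10-year group takes in adult catch-up. Given the protocol's expectation of better protection after younger vaccination, the expected bias is towards hiding waning. Under the assumed 88% and 38%, a fall to 70% is reversed once more than 36% of the ≤10-year mothers were vaccinated older and none of the >10-year mothers were. A larger older share in the >10-year group reduces this. The shares, the age-specific effectiveness and the amount of waning are all assumptions, so the size is illustrative.

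A reader might also infer that the main effectiveness result is biased, or that the durability table must have the wrong sign. Neither follows. The primary comparison does not use time since vaccination, and the sign depends on shares the documents do not give. This is a flaw in a stated secondary analysis, worth correcting because it costs only wording.

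**What to change.** In sections 7.2.3 and 7.8.2 and in note 2 to Table 3:

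- State that time since vaccination is measured to delivery.
- Present it within age-at-vaccination strata, at least for mothers vaccinated <17 at ≤10 and >10 years, each against unvaccinated mothers.
- Draw any durability statement from that contrast and not from the unstratified table. If the unstratified table is kept, label it as confounded by age at vaccination.
- Report the ≥17, >10-year cell only if observed counts allow.
- Note that the contrast within <17 is still tied to maternal age at delivery.

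No new data are needed. The cost is precision: with about 3-7 vaccinated cases in all on the protocol's assumptions, intervals will be wide, exact counts may be withheld, and the result may be reportable only as inconclusive.
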